7.6.5 Progression-free survival (PFS) and overall survival

Progression-free survival (PFS) is defined as the time from the date of start of treatment until the date of first documented confirmed disease progression or death or institution of new therapy. If a patient did not progress or die due to any cause at the time of the analyses, PFS will be censored at the date of the last adequate response assessment. Kaplan-Meier product-limit estimates will be used to summarize PFS. For overall survival, patients will be contacted every 6 months until the study closure or death.

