3.2 Discussion of design

Patients will receive open label SGN-35 at a starting dose of 1.8 mg/kg administered as a single IV infusion as on Day 1 of each 21-day cycle as an outpatient. Patients will be treated for eight 21-day cycles. The best response per international response criteria will be recorded by the end of cycle 8. Because responses must last at least 12 weeks, any clinical improvement (CI), partial response (PR), or CR response that commences by the end of cycle 8, and either persists or evolves into a higher quality response for at least 12 weeks will be counted as a response. Patients who demonstrate a response and subsequently meet criteria for loss of response (LOR) will be permitted to undergo re-staging and re-treatment with up to an additional 8 cycles of SGN-35.

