- Evaluate for adverse events

End-of-Treatment (End of Cycle 8) Visit

- Evaluate for adverse events
- Interval medical history including transfusion history
- Current medications
- Physical exam, including measurement of spleen, weight, and vital signs
- ECOG performance Status
- MPN-SAF modified for mast cell symptoms
- Hematology, chemistries/liver function tests, serum tryptase, PT, PTT (**Please refer to section 4.8.1 for detailed lab evaluations**)
- Pregnancy test (women of child bearing potential)
- MRI or CT of abdomen/pelvis with and without contrast including 3D spleen and liver volumes
- Chest x-ray 2 views - PA and lateral (only if disease related finding(s) were found at baseline)
- Bone marrow aspirate and biopsy with cytogenetics, flow cytometry, *KIT* mutation status
- Response assessment per IWG-MRT-ECNM criteria Drug Accountability

End of Study (EOS) Visit - if no response to the study drug after 8 cycles of treatment, one follow-up visit about 30 days after the end-of-treatment visit

- Evaluate for adverse events

- Interval medical history including transfusion history
- Current medications
- Physical exam, including measurement of spleen, weight, and vital signs
- ECOG performance status
- MPN-SAF modified for mast cell symptoms
- Hematology, chemistries/liver function tests, serum tryptase (**Please refer to Section 4.8.1 for detailed lab evaluations**)
- Pregnancy Test (women of child bearing potential)
- Response assessment per IWG-MRT-ECNM criteria

Follow-up visits - if patient did exhibit a response to the study drug after 8 cycles of treatment according to protocol response criteria, follow-up visits and labs every 6 weeks until 48 weeks from beginning of treatment will occur, then every 12 weeks.

- Evaluate for adverse events
- Interval medical history including transfusion history
- Current medications
- Physical exam, including measurement of spleen, weight, and vital signs
- ECOG performance status
- MPN-SAF modified for mast cell symptoms
- Hematology, chemistries/liver function tests, serum tryptase (**Please refer to Section 4.8.1 for detailed lab evaluations**)
- Bone Marrow aspirate and biopsy, cytogenetics, flow cytometry, *KIT* mutation status (at week 48, then every 24 weeks)
- MRI or CT of abdomen/pelvis with and without contrast including 3D spleen and liver volumes (at week 48, then every 24 weeks)
- Drug accountability
- Response assessment per IWG-MRT-ECNM criteria

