- ECOG performance Status
- MPN-SAF modified for mast cell symptoms
- Hematology, chemistries/liver function tests, serum tryptase (**Please refer to section 4.8.1 for detailed lab evaluations**)
- Bone Marrow aspirate and biopsy, cytogenetics, flow cytometry, *KIT* mutation status (at week 48 from day 1 of re-treatment, then every 24 weeks)
- MRI or CT of abdomen/pelvis with and without contrast including 3D spleen and liver volumes (at week 48 from re-treatment, then every 24 weeks)
- Response assessment per IWG-MRT-ECNM criteria

There will not be any additional treatments after completion of the drug infusion at start of cycle 16. Patient will come for follow up visits per the schedule above as long as they show response. At the time of loss of response, patient will have an end of study visit (with the same assessments as at the end of study (EOS) visit for patients with no response at end of cycle 8 or 16) and will be taken off the study.

Long-term survival:

All patients will be followed every 6 months for survival until study closure or death of the patient.

Table 2. Visit and Assessment Schedule

	Screen	Assessments within +/- 3 days						End of Treatment (EOT) (@ completion of 8 cycles of therapy)	Day +30 after EOT for non-responders (g)	Maintenance labs and visits after 8 cycles for ongoing responders (h)	Re-Staging for pts who exhibit loss of response (LOR)	Re-Treatment Cycles 9-16 ^(a) for pts who exhibit loss of response (LOR)	Long Term Survival ^(j)
		Cycle 1			Cycle 2-8								
Evaluation	Day -28 to Day -1	Day 1 ^(b)	Day 3 (can be local)	Day 8 (can be local)	Day 15 (can be local)	Day 1	Day 10 (can be local)	(EOT)	(EOS)	Labs and visits q 6 weeks up to week 48; then q 12 weeks	Day -21 to Day -1	Repeat schedule of original cycles 1, 2-8 and EOT (except PT, PTT)	
Informed consent/eligibility criteria	X												
Complete medical history	X												
Interval medical history		X				X		X	X	X	X		
Prior and concomitant medications	X	X				X		X	X	X	X		
Transfusion history in prior 12 weeks	X	X				X		X	X	X	X		
Vital signs, physical exam, body weight, height ⁽ⁱ⁾	X ⁽ⁱ⁾	X				X		X	X	X	X		
ECOG performance status	X	X				X		X	X	X	X		
MPN-SAF, QOL questionnaires	X	X				X		X	X	X	X		
12-lead ECG	X												
Hematology ^(c)	X	X		X	X	X	X	X	X	X	X		
Serum chemistries/liver function tests ^(c)	X	X	X	X	X	X		X	X	X	X		
Serum tryptase level	X	X				X		X	X	X	X		
PT and PTT	X	X				X		X					
Pregnancy test	X	X				X		X	X		X		

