- d If disease-related findings are found on chest x-ray (2 views PA and lateral) (eg, pleural effusion), then an x-ray will be performed at the end of cycles 4 and 8 or EOT, whichever comes first, and at the time of progressive disease or loss of response (LOR). Chest X-ray (2 views-PA and lateral) will also be performed at the time of re-staging. If disease-related findings are found on chest x-ray (eg, pleural effusion) at the time of re-staging, then an x-ray will be performed at the end of cycles 12 and 16 or EOT, whichever comes first, and at the time of progressive disease or loss of response (LOR). Interval chest x-rays can be performed at the discretion of the investigator.
- e Besides screening, marrows will be performed at the end of cycles 4 and 8 or EOT, whichever comes first, and at the time of progressive disease or loss of response (LOR). A repeat bone marrow aspirate and biopsy should be performed at the end of week 48 and every 6 months thereafter in ongoing responders. Please refer to section 4.9 Central Histopathology Review for items required with bone marrow biopsy and aspiration.
- f MRI (or CT scan) abdomen/pelvis with and without contrast including 3-D spleen and liver volumes will be obtained at screening, at the end of cycle 4, and at the end of cycle 8 or EOT, whichever comes first, and at the time of progressive disease or loss of response (LOR). Interval MRI or CT scans can be performed at the discretion of the investigator. A repeat MRI or CT should be performed at the end of week 48 and every 6 months thereafter in ongoing responders.
- g A visit on day +30 will be conducted after the EOT visit for follow-up for non-responders. This will be end of study visit (EOS)
- h After 8 cycles of therapy are completed, labs and visits with the trial site every 6 weeks up to week 48; then every 12 weeks.
- i Height is to be obtained only at screening.
- j Long Term Survival: every 6 months after end of study visit until study closure or death of the patient.

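### PFS counts deaths at any time but censors survivors at their last response assessment, so the all-patient curve after about day 199 depends on the closure date and cannot be interpreted

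*Combined protocol and SAP*

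**What the plan says.** Section 7.6.5 runs PFS from the start of treatment "until the date of first documented confirmed disease progression or death or institution of new therapy". Its censoring sentence begins "If a patient did not progress or die due to any cause at the time of the analyses" and ends "PFS will be censored at the date of the last adequate response assessment". The estimator is fixed: "Kaplan-Meier product-limit estimates will be used to summarize PFS".

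The schedule sets how far response assessment reaches. Section 3.2 states "Patients will be treated for eight 21-day cycles". Section 4.6.1 provides, "if no response to the study drug after 8 cycles of treatment, one follow-up visit about 30 days after the end-of-treatment visit", and footnote g of Table 2 makes this the end-of-study visit. After it comes survival contact only: "All patients will be followed every 6 months for survival until study closure or death of the patient". Ongoing responders are assessed every 6 weeks to week 48 and every 12 weeks after that. Section 4.3 places early discontinuers on 6-monthly survival follow-up.

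No section limits how long after the last assessment a death still counts as a PFS event, gives a rule for deaths after missed assessments, or fixes a PFS data cut-off.

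**The concern.** Take two non-responders, both alive and progression-free at day 199. One dies in month 20, so he is an event at month 20 and is at risk until then. The other is alive in month 20 and at closure, so he is censored back at day 199. They differ only in what happened after day 199, yet that decides whether they were in the risk set in between. Kaplan-Meier requires that leaving the risk set does not depend on the later outcome.

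PFS is a named secondary objective. Even at the 30% response rate of the design's alternative, most patients are non-responders, so the rule governs most of the curve after day 199. An estimate for 12 or 24 months would then change with the closure date although no disease information had been added.

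**Working it through.** **1. The horizon.** Treatment lasts 8 × 21 = 168 days, so end of treatment is nominally day 169. Adding 30 days gives day 199, about 6.5 months (199 / 30.4). It is earlier for early discontinuers and later when cycles are delayed (section 4.2.5 allows up to 30 days).

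**2. The plan's own figure.** The documents state no PFS estimate, hazard, accrual time or closure date, so there is nothing to reproduce. Everything below rests on stated assumptions.

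**3. Hand example (assumed data).** There are 26 patients: 6 responders without events who are assessed to closure, and 20 non-responders. Six non-responders progress by day 199, so S(199) = 20/26 = 0.769. The other 14 are stable at the end-of-study visit, and six of them die, on days 300, 420, 520, 640, 760 and 900. Under the plan the risk set at day 300 is the 6 responders plus the non-responders who die before closure.

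| Closure | At risk, day 300 | S(520), plan |
|---|---|---|
| day 540 | 6 + 3 = 9 | 0.769 × 6/9 = 0.513 |
| day 800 | 6 + 5 = 11 | 0.769 × 8/11 = 0.559 |
| day 1009 | 6 + 6 = 12 | 0.769 × 9/12 = 0.577 |

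If survivors are instead censored when last known alive, 20 are at risk at day 300, and S(520) = 0.769 × 17/20 = 0.654 at all three closures. That comparator only isolates the effect of the censoring rule. It is not a valid PFS curve either, because progression after day 199 is still unobserved.

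**4. Scenario without progression (simulation).** Assumed: 26 patients, 6 responders assessed to closure, 20 non-responders last assessed at day 199, and exponential survival with a 24-month median in both groups. True 24-month PFS is 50% and the true median is 24 months. With closure at 24, 36 and 60 months the plan averages 22%, 34% and 44%, with a median of about 15, 17 and 20 to 21 months.

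**5. Scenarios with progression (simulation).** Assumed: 10% response; median time to death without progression 24 months; median survival after progression 9 months; responder progression median 36 months (none in the first row); 18-month accrual. With non-responder progression median P months, true 18-month PFS is 0.9 × 2^−(18/24 + 18/P) + 0.1 × 2^−(18/24 + 18/36). For P = 12 this is 0.9 × 0.210 + 0.1 × 0.420 = 0.23.

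18-month PFS:

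| P | Plan, closure 24 / 36 / 48 / 60 months | Known-alive censoring, closure 36 | True |
|---|---|---|---|
| none | 0.179 / 0.358 / 0.464 / 0.518 | 0.593 | 0.595 |
| 24 | 0.128 / 0.288 / 0.383 / 0.421 | 0.452 | 0.36 |
| 12 | 0.114 / 0.245 / 0.318 / 0.347 | 0.363 | 0.23 |
| 6 | 0.089 / 0.173 / 0.220 / 0.234 | 0.240 | 0.11 |

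Every row moves with closure. With closure at 36 months the plan lies below the known-alive curve in every row. Against the truth the sign is mixed. For P = 12 and closure at 36 months the plan is too high at 12 months (0.420 against 0.375) and too low at 30 months (0.036 against 0.091). For P = 6 it is too high at 12 months (0.304 against 0.215) and at 18 months (0.173 against 0.109).

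**The case against.** A reader might infer that the PFS curve is simply too low. The documents do not support that. The schedule that creates the censoring problem also stops looking for progression in non-responders, so later progressions are missed or are dated at death, which raises the curve. Step 5 shows that the net error can have either sign. Only the comparison with a consistently censored curve has a fixed direction.

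A reader might also infer that the median is always distorted. It is not: if half the patients have had an event by about day 199, the median is unaffected.

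The size in step 4 can be challenged too. It assumes no progression, one hazard for both groups and 26 patients, whereas the current study enrols 11 and stage 2 needs an amendment. It is an illustration and not a forecast.

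The strongest objection is to the obvious repair. Changing only the censoring date leaves a late curve made of responders alone. With assumed median survival of 48 months in responders and 18 months in non-responders, no progression and closure at 36 months, true 24-month PFS is (6/26) × 2^−(24/48) + (20/26) × 2^−(24/18) = 0.163 + 0.305 = 0.47. The plan gives about 0.30 and the date-only repair about 0.61. This objection stands, and the fix has to limit the reporting period as well.

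None of these points makes the stated rule valid. Two opposing biases of unknown size do not produce an estimate.

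**Conclusion.** The point holds in this form. Under 7.6.5, after nominal day 199, the non-responders left in the risk set are essentially those who die before closure. The possible exception is a patient who starts new therapy, if that is recorded after the end-of-study visit, although the schedule lists survival only. The curve beyond that day moves with the closure date, its error against true PFS has no known direction, and it should not be interpreted. The same applies to the median if it falls there. Responders have the same asymmetry on a smaller scale, with a gap of 6 to 12 weeks that widens once they leave the study.

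The mechanism and the closure dependence follow from the text and the schedule. The sizes rest on assumed hazards, accrual and closure. In the scenarios simulated, the estimate agreed with the truth up to the common horizon. PFS is secondary and descriptive, and the primary response analysis, the sample size and the two-stage decision rule are untouched. It should be corrected before PFS is analysed.

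**What to change.** State three things in section 7.6.5.

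1. PFS observation ends for each patient at the last adequate response assessment plus one scheduled assessment interval, and no later than a stated data cut-off. The intervals should be listed: 21 days on treatment, about 30 days from end of treatment to the end-of-study visit, 6 weeks to week 48, and 12 weeks thereafter. Deaths up to that date are events. Patients alive on that date, or dying later, are censored there, and later deaths count in overall survival only.
2. The all-patient curve and estimates are reported only to the end of the common assessment schedule, nominal day 199. A median beyond it is given as not reached within the assessed period.
3. Later disease control is described in responders only, through duration of response, and is labelled as such.

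The cost is analysis wording and one derived date per patient. There would be fewer PFS events and no all-patient PFS estimate beyond about 6.5 months. Early discontinuers are still censored before the horizon, so their number and reasons should be reported beside the curve. If a longer all-patient PFS is wanted, wording cannot supply it: response assessment and recording of new therapy would have to continue in everyone until progression or closure, which means added visits.

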7.7 Interim analyses

An interim analysis will be provided after enrolling 11 evaluable patients, as described in Section 7.8.

7.8 Sample size and power considerations

A study of brentuximab vedotin (SGN-35) in CD30-positive systemic mastocytosis with or without an associated hematological clonal non-mast cell lineage disease (AHNMD)

The primary endpoint is response rate per international consensus response criteria (see Appendix G).

The trial will be carried out as a Simon two-stage Optimum design with a total *potential* sample size of 26 patients (Simon R, 1989). The first stage will be this investigator-initiated phase II study of 11 patients. We assume that the probability of accepting the treatment when the true response rate is $\leq 10\%$ is less than or equal to 10%, and the probability of rejecting the treatment when the true response rate is $\geq 30\%$ is less than or equal to 15%.

Under these assumptions, the stopping rules are as follows: Accrue a cohort of 11 patients in this first stage phase II study. If 2 or more patients out of 11 respond, the study will be amended to enroll an additional 15 patients in the second stage. If less than 2 responses are seen, the study will be halted. At the end of the second stage, if 5 or more patients out of 26 respond, the regimen will be considered for further investigation in the treatment of advanced mastocytosis. With this design, the chance of falsely claiming that regimen is efficacious (alpha) is 8.7%, and the power is 85%. The probability of stopping early is 70% under the null hypothesis of a 10% response rate is 10%; it is 11% if the true response rate is 30%.

8 Procedures and instructions

8.1 Special safety-related procedures

Adverse Event

An *adverse event* (AE) is any symptom, sign, illness or experience that develops or worsens in severity during the course of the study. Intercurrent illnesses or injuries should be regarded as adverse events. Abnormal results of diagnostic procedures are considered to be adverse events if the abnormality:

- results in study withdrawal
- is associated with a serious adverse event
- is associated with clinical signs or symptoms
- leads to additional treatment or to further diagnostic tests
- is considered by the investigator to be of clinical significance

Serious Adverse Event

Adverse events are classified as serious or non-serious. A *serious adverse event* is any AE that is:

- fatal
- life-threatening
- requires or prolongs hospital stay
- results in persistent or significant disability or incapacity
- a congenital anomaly or birth defect
- an important medical event

Important medical events are those that may not be immediately life threatening, but are clearly of major clinical significance. They may jeopardize the subject, and may require intervention to prevent one of the other serious outcomes noted above. For example, drug overdose or abuse, a seizure that did not result in in-patient hospitalization, or

intensive treatment of bronchospasm in an emergency department would typically be considered serious. All adverse events that do not meet any of the criteria for serious should be regarded as *non-serious adverse events*.

Adverse Event Reporting Period

The study period during which adverse events must be reported is normally defined as the period from the initiation of any study procedures to the end of the study treatment follow-up. For this study, the study treatment follow-up is defined as 30 days following the last administration of study treatment.

Preexisting Condition

A preexisting condition is one that is present at the start of the study. A preexisting condition should be recorded as an adverse event if the frequency, intensity, or the character of the condition worsens during the study period.

General Physical Examination Findings

At screening, any clinically significant abnormality should be recorded as a preexisting condition. At the end of the study, any new clinically significant findings/abnormalities that meet the definition of an adverse event must also be recorded and documented as an adverse event.

Post-study Adverse Event

All unresolved adverse events should be followed by the investigator until the events are resolved, the subject is lost to follow-up, or the adverse event is otherwise explained. At the last scheduled visit, the investigator should instruct each subject to report any subsequent event(s) that the subject, or the subject's personal physician, believes might reasonably be related to participation in this study. The investigator should notify the study sponsor of any death or adverse event occurring at any time after a subject has discontinued or terminated study participation that may reasonably be related to this study. The sponsor should also be notified if the investigator should become aware of the development of cancer or of a congenital anomaly in a subsequently conceived offspring of a subject that has participated in this study.

Abnormal Laboratory Values

A clinical laboratory abnormality should be documented as an adverse event if any one of the following conditions is met:

- The laboratory abnormality is not otherwise refuted by a repeat test to confirm the abnormality
- The abnormality suggests a disease and/or organ toxicity
- The abnormality is of a degree that requires active management; eg, change of dose, discontinuation of the drug, more frequent follow-up assessments, further diagnostic investigation, etc.

Hospitalization, Prolonged Hospitalization or Surgery

Any adverse event that results in hospitalization or prolonged hospitalization should be documented and reported as a serious adverse event unless specifically instructed otherwise in this protocol. Any condition responsible for surgery should be documented as an adverse event if the condition meets the criteria for an adverse event.

Neither the condition, hospitalization, prolonged hospitalization, nor surgery are reported as an adverse event in the following circumstances:

- Hospitalization or prolonged hospitalization for diagnostic or elective surgical procedures for a preexisting condition. Surgery should **not** be reported as an outcome of an adverse event if the purpose of the surgery was elective or diagnostic and the outcome was uneventful.
- Hospitalization or prolonged hospitalization required to allow efficacy measurement for the study.
- Hospitalization or prolonged hospitalization for therapy of the target disease of the study, unless it is a worsening or increase in frequency of hospital admissions as judged by the clinical investigator.

Recording of Adverse Events

At each contact with the subject, the investigator must seek information on adverse events by specific questioning and, as appropriate, by examination. Information on all adverse events should be recorded immediately in the source document, and entered on the appropriate case report form (CRF). All clearly related signs, symptoms, and abnormal diagnostic procedures results should be recorded in the source document, though should be grouped under one diagnosis.

All adverse events occurring during the study period must be recorded. The clinical course of each event should be followed until resolution, stabilization, or until it has been determined that the study treatment or participation is not the cause. Serious adverse events that are still ongoing at the end of the study period must be followed up to determine the final outcome. Any serious adverse event that occurs after the study period and is considered to be possibly related to the study treatment or study participation should be recorded and reported immediately.

